10.1.2.3.2. Studies with paper diaries

For studies using paper diaries which have questions in the CRF indicating the presence or absence of solicited symptoms, the following rules are applicable.

Denominators for the summary of local (or general) solicited symptoms will be calculated using the number of subjects who respond "Yes" or "No" to the question concerning the occurrence of local (or general) symptoms.

When a specific symptom is marked as having not occurred following a specific vaccination for the specified post-vaccination period for the symptom in question, all daily measurements will be imputed as Grade 0.

When a specific symptom is marked as having occurred following a specific vaccination for the specified post-vaccination period for the symptom in question, any missing daily recordings will be given imputed values to allow them to contribute to the ‘Any’ rows but not to specific grade rows of the symptom summary tables.

When the occurrence of a specific symptom is not present (for the specified post-vaccination period for the symptom in question) but the group of symptoms (local or general) is marked as having occurred, all missing daily recordings will be given imputed values to allow them to contribute to the ‘Any’ rows but not to specific grade rows of the symptom summary tables.

The following table shows how subjects contribute to each category for a specific solicited symptom over the Day 0 to Day 3 post-vaccination period:

Solicited symptom category	Subjects included in the calculation of the numerator
Any	All subjects with at least one occurrence of the symptom at grade 1, grade 2, or grade 3 between Day 0 and Day 3 or with the symptom marked as present and at least one missing daily recording between Day 0 and Day 3
At least grade 1	All subjects with at least one occurrence of the symptom at grade 1, grade 2, or grade 3 between Day 0 and Day 3
At least grade 2	All subjects with at least one occurrence of the symptom at grade 2 or grade 3 between Day 0 and Day 3
At least grade 3	All subjects with at least one occurrence of the symptom at grade 3 between Day 0 and Day 3

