For a given subject and the analysis of solicited adverse events within 4 days post-vaccination, missing or non-evaluable measurements will not be replaced. Therefore, the analysis of the solicited adverse events based on the Total Vaccinated Cohort will include only vaccinated subjects for doses with documented safety data (i.e., symptom screen completed). More specifically the following rules will be used:

- Subjects who documented the absence of a solicited adverse events after one dose will be considered not having that adverse events after that dose.
- Subjects who documented the presence of a solicited symptom and fully or partially recorded daily measurement over the solicited period will be included in the summaries at that dose and classified according to their maximum observed daily recording over the solicited period.
- Subjects who documented the presence of a solicited symptom after one dose without having recorded any daily measurement will be assigned to the lowest intensity category at that dose (i.e., 37.5°C for fever or grade 1 for other symptoms).
- Doses without symptom sheets documented will be excluded.

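### The SAP gives two unreconciled rules for a solicited symptom marked present with missing diary days, and does not say which one governs

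*SAP*

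**What the plan says.** Both rules stand in SAP 10.1.2.3.2, and each is introduced as the rule in force.

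**Table rule (opening paragraphs and numerator table).** Once a symptom is marked as having occurred, "any missing daily recordings will be given imputed values to allow them to contribute to the ‘Any’ rows but not to specific grade rows". The table is introduced as showing "how subjects contribute to each category for a specific solicited symptom over the Day 0 to Day 3 post-vaccination period". Its *Any* category takes in infants with a recorded grade of 1 to 3 and also those "with the symptom marked as present and at least one missing daily recording between Day 0 and Day 3". Its *At least grade 1* category is narrower: "All subjects with at least one occurrence of the symptom at grade 1, grade 2, or grade 3 between Day 0 and Day 3". A missing day does not qualify for it.

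**Bullet rule (closing paragraph and bullets).** Here "missing or non-evaluable measurements will not be replaced". The second bullet covers a symptom documented as present with a full or partial diary: the infant is "included in the summaries at that dose and classified according to their maximum observed daily recording over the solicited period". The third covers a symptom documented as present where no day was filled in: an infant "without having recorded any daily measurement will be assigned to the lowest intensity category at that dose", given as 37.5 °C for fever and grade 1 for the other symptoms.

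**Elsewhere.** The no-replacement sentence also appears in SAP 5.4.1 and in Protocol 10.5, in both cases under handling of missing data, without saying how a partial diary is graded. SAP 10.1 says its rules apply together with those of section 9, and section 9 has nothing on solicited symptoms.

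**The concern.** The same diary can meet both rules and come out differently. One rule imputes missing days so that the infant stays in *Any*. The other replaces nothing and grades on what was observed. They part where the parent ticked the symptom as present but the daily grid does not show it, because the recorded days are all zero with a gap or because no day was recorded.

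Occurrence of solicited symptoms over Day 0 to Day 3 is a secondary endpoint (Protocol 10.2, SAP 3.4). Two programmers could each follow the SAP and report different numerators. Under one reading, a symptom that the parent documented, and that may have occurred on the missing day, is not counted at all.

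**Working it through.** There is no planned figure to reproduce, so the check applies both rules to every possible diary.

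**Inputs**
- Four daily recordings, Day 0 to Day 3 (SAP 10.1.2.3.2).
- Each day is grade 0, 1, 2, 3 or missing, and the symptom is marked present.
- Table rule: *Any* if some recorded day is grade 1 or higher, or if any day is missing. The grade rows depend on recorded grades only.
- Bullet rule, read literally: grade is the maximum recorded day, or grade 1 if no day is recorded. *Any* requires grade 1 or higher.

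**Enumeration**
- All diaries: 5^4 = 625. Complete diaries: 4^4 = 256. Incomplete diaries: 625 − 256 = 369.
- Type A (at least one recorded day, all recorded days grade 0, at least one missing): 2^4 − 2 = 14 patterns.
- Type B (all four days missing): 1 pattern.
- The rules disagree on 14 + 1 = 15 incomplete patterns. They agree on the other 369 − 15 = 354, each of which has a recorded grade of 1 or more, and on all 256 complete diaries.

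| Symptom marked present, Days 0–3 | Table rule | Bullet rule, read literally |
|---|---|---|
| A: 0, 0, 0, missing | *Any* yes, no grade row | Maximum grade 0, *Any* no |
| B: all four missing | *Any* yes, *At least grade 1* no | *Any* yes, *At least grade 1* yes |
| 0, 1, missing, 0 | *Any* yes, *At least grade 1* yes | Same |
| 0, 0, 0, 0 | *Any* no | Same |

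**Which output rows move**
- Type A bears on the All rows of Templates 18 and 19, taking All to be the *Any* category.
- Type B bears only on *At least grade 1*. Template 18 shows All, Grade 3 and Medical advice. For symptoms other than temperature, Template 19 shows All, Grade 2 or 3, Grade 3, two rows on relatedness and Medical advice. Neither has an *At least grade 1* row.
- For fever, a value of exactly 37.5 °C does not enter Template 19's first threshold row (>37.5). It is grade 1 on the oral, axillary and tympanic scale (Protocol 8.2.3.2.1) but grade 0 on the rectal scale (below 38 °C, SAP 10.1.3.5), so it is not the lowest fever grade for every route.

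**Size per record**
- Templates 16 and 18 illustrate 330 symptom sheets in the dTpa group. One reclassified infant moves a rate by 1/330 = 0.30 percentage points.
- For scale, the illustrative swelling row is 98/330 = 29.7%. With one infant fewer it is 97/330 = 29.4%.

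**The case against.** The strongest reply concerns type A. The bullets never say that a symptom documented as present is scored as absent. The first bullet reserves that outcome for infants whose absence of the symptom was documented. The second can be read as an intensity rule only, with the numerator table deciding who belongs in *Any*. On that reading the infant is in *Any* with no grade row, and the two passages agree. This stands as a possible reconciliation, but the SAP does not state it. The more natural reading of a classification at maximum grade 0 is no event, so type A is an ambiguity with a real consequence rather than a flat contradiction. Type B is a literal conflict on any reading, though it changes no row in Templates 18 or 19.

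Three further points limit the consequence. Site staff collect and verify the diary cards with the parent at Visit 3 (Protocol 5.6.2.14), and omissions or inconsistencies may be sent back for correction (Protocol 11.1), so such diaries should be uncommon. All analyses are descriptive (SAP section 6), and either rule would apply alike to both groups. The 330 comes from mock tables copied from other studies (SAP section 12).

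A reader might infer that the reported *Any* rates will be biased downward by a material amount. The documents do not support that. They give no share of incomplete diaries from which to work out a total, and the downward shift arises only under the literal reading of the second bullet.

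**Conclusion.** The point holds as an inconsistency in the SAP's rules, with no stated precedence. Type A can remove a documented symptom from the All rows, on the assumption that a maximum of grade 0 under the bullets means no event. Type B changes the table's *At least grade 1* category and nothing shown in Templates 18 or 19.

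The supported size is about 0.3 points per type A record at the illustrative 330 sheets. The total depends on a count the documents do not give and is probably small. The case for acting is that the counts should not depend on which paragraph the programmer follows.

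**What to change.** - State in SAP 10.1.2.3.2 that the numerator table governs.
- Align the second and third bullets with it, for example: *a symptom marked present with at least one missing day and no recorded day at grade 1 to 3 counts in Any with grade unknown, and in no grade row.* For these records this replaces the lowest-intensity assignment, and with it the 37.5 °C value that does not fit the rectal scale.
- Footnote the number of infants with unknown grade in the solicited-symptom tables.
- Record in SAP section 8 that this clarifies the no-replacement sentence in SAP 5.4.1 and Protocol 10.5. Editing the annex alone would leave it at odds with both.

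The cost is SAP wording, with no new data. The downside is that a small grade-unknown count appears in the tables.

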**Table 14 Intensity scales for solicited symptoms**

Adverse Event	Intensity grade	Parameter
Pain at injection site	0	None
	1	Mild: Minor reaction to touch
	2	Moderate: Cries/protests on touch
	3	Severe: Cries when limb is moved/spontaneously painful
Redness at injection site		Record greatest surface diameter in mm
Swelling at injection site		Record greatest surface diameter in mm
Fever*		Record temperature in °C/°F
Irritability/Fussiness	0	Behaviour as usual
	1	Mild: Crying more than usual/no effect on normal activity
	2	Moderate: Crying more than usual/interferes with normal activity
	3	Severe: Crying that cannot be comforted/prevents normal activity
Drowsiness	0	Behaviour as usual
	1	Mild: Drowsiness easily tolerated
	2	Moderate: Drowsiness that interferes with normal activity
	3	Severe: Drowsiness that prevents normal activity
Loss of appetite	0	Appetite as usual
	1	Mild: Eating less than usual/no effect on normal activity
	2	Moderate: Eating less than usual/interferes with normal activity
	3	Severe: Not eating at all

\*Fever is defined as temperature  $\geq 37.5^{\circ}\text{C}/99.5^{\circ}\text{F}$  for oral, axillary or tympanic route, or  $\geq 38.0^{\circ}\text{C}/100.4^{\circ}\text{F}$  for rectal route. The preferred route for recording temperature in this study will be axillary/rectal.

The maximum intensity of local injection site redness/swelling will be scored at GSK Biologicals as follows:

- 0 : Absent
- 1 :  $\leq 5$  mm
- 2 :  $> 5$  mm and  $\leq 20$  mm
- 3 :  $> 20$  mm

The maximum intensity of fever (*oral, axillary or tympanic route*) will be scored at GSK Biologicals as follows: (Amended 12 December 2016)

- 0 =  $< 37.5^{\circ}\text{C}$
- 1 =  $\geq 37.5^{\circ}\text{C}$  to  $\leq 38.0^{\circ}\text{C}$
- 2 =  $> 38.0^{\circ}\text{C}$  to  $\leq 39.0^{\circ}\text{C}$
- 3 =  $> 39.0^{\circ}\text{C}$

The investigator will assess the maximum intensity that occurred over the duration of the event for all unsolicited AEs (including SAEs) recorded during the study. The assessment will be based on the investigator's clinical judgement.

The intensity should be assigned to one of the following categories:

- 1 (mild) = An AE which is easily tolerated by the subject, causing minimal discomfort and not interfering with everyday activities.
- 2 (moderate) = An AE which is sufficiently discomforting to interfere with normal everyday activities.

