10.1.3.5. Temperature

- Temperatures will be presented in degrees Celsius (°C). Temperatures reported in degrees Fahrenheit (°F) will be converted as follows:

$$\text{Temperature (Celsius)} = ((\text{Temperature (Fahrenheit)} - 32) \times 5) / 9$$

The result is rounded to 1 decimal.

- The intensity of fever measured by oral, axillary or tympanic route will be scored as defined in the protocol. If in case, measured by rectal route, then the scoring will be performed as below to integrate the results with the other routes.

0	<38°C
1	≥38.0°C to ≤39.0°C
2	>39.0°C to ≤40.0°C
3	>40.0°C

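### The 37.5°C assigned to a fever with no recorded temperature is grade 0 on the SAP's rectal scale, and the SAP disagrees with itself on whether such fevers enter the grade rows

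*SAP*

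**What the plan says.** SAP 10.1.2.3.2 (Studies with paper diaries) handles incomplete diary data in two places.

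- The first part, which contains the numerator table, covers a symptom marked as having occurred with daily values missing: "any missing daily recordings will be given imputed values to allow them to contribute to the ‘Any’ rows but not to specific grade rows". The table's 'Any' category includes an infant "with the symptom marked as present and at least one missing daily recording between Day 0 and Day 3". Neither a temperature nor a route is required.
- The list that closes the section separates infants with full or partial daily recordings, who are classified by their highest observed value, from infants with none. An infant with none "will be assigned to the lowest intensity category at that dose (i.e., 37.5°C for fever or grade 1 for other symptoms".

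Two other places set the scale on which a temperature is graded.

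- Protocol Table 14 (section 8.2.3.2.1) starts fever at 37.5°C for oral, axillary and tympanic readings and at 38.0°C for rectal readings. Its footnote adds: "The preferred route for recording temperature in this study will be axillary/rectal".
- SAP 10.1.3.5 gives rectal readings their own scale: "If in case, measured by rectal route, then the scoring will be performed as below to integrate the results with the other routes". Grade 0 is anything below 38°C, and grade 1 is "≥38.0°C to ≤39.0°C".

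**The concern.** The assignment rule has a clear purpose: a symptom the parent reported, but did not measure, should count at the mildest positive grade. For every other solicited symptom it does so, at grade 1. For fever it gives a temperature instead of a grade, and that temperature is the mildest positive one only on the oral, axillary and tympanic scale. On the rectal scale it is not a fever. Rectal is one of the two routes the protocol prefers, so this is not a remote case.

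Fever is a solicited event within a secondary endpoint (Protocol 10.2). Protocol 6.6 warns of more febrile reactions when *Infanrix hexa* is given with a pneumococcal conjugate vaccine, which every infant here receives. Protocol 10.8 and SAP 5.4.1 tabulate fever in cumulative 0.5°C steps, so an imputed temperature could feed the tables directly. At stake are the graded and temperature-based fever rows, and whether the same report is treated alike by both preferred routes.

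**Working it through.** No sample-size or power figure is involved. The check applies the documents' own scales and counting rules to the imputed value.

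**Inputs**

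- Imputed value: 37.5°C, no route stated (SAP 10.1.2.3.2).
- Oral, axillary and tympanic scale (Protocol Table 14): grade 0 below 37.5; grade 1 from 37.5 to 38.0; grade 2 above 38.0 to 39.0; grade 3 above 39.0.
- Rectal scale (SAP 10.1.3.5): grade 0 below 38.0; grade 1 from 38.0 to 39.0; grade 2 above 39.0 to 40.0; grade 3 above 40.0.
- 'Any' (numerator table): grade at least 1 on some day, OR symptom marked present AND at least one of the four daily recordings missing.
- 'At least grade 1' (same table): grade at least 1 on some day.
- Lowest temperature threshold row in Template 19 (SAP Annex 3): strictly above 37.5°C.

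**Step 1: reproduce the plan's figure.** On the oral, axillary and tympanic scale the lower bound of grade 1 is 37.5°C, so the stated value is that scale's lowest positive category. On the rectal scale the lower bound is 38.0°C, and 37.5°C does not reproduce.

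**Step 2: apply the rules to a fever marked present with all four recordings missing.**

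| Imputed value, scale | Grade | Meets fever definition | 'Any' | 'At least grade 1' from the imputed value | Template 19 row above 37.5 |
|---|---|---|---|---|---|
| 37.5, oral/axillary/tympanic | 1 | yes | yes | yes | no |
| 37.5, rectal | 0 | no (37.5 < 38.0) | yes (4 missing ≥ 1) | no | no |
| 38.0, rectal | 1 | yes | yes | yes | yes |

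**Step 3: read the table.** The 'Any' result is the same in every line, because the marked-present condition is met without a temperature. The two routes part at 'At least grade 1', and would also part in any program that derives fever from the imputed temperature alone.

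**Step 4: compare the two parts of SAP 10.1.2.3.2.** The first part keeps missing recordings out of the specific grade rows. The closing list assigns an intensity category. For an infant with no daily value at all, one part says no grade and the other says the lowest grade. This holds for every route and every graded symptom, and the SAP does not say which part prevails.

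**Step 5: test a route-specific temperature as the remedy.** With 38.0°C for rectal and 37.5°C for the other routes, the grades agree. If raw imputed values feed Template 19, however, the rectal infant enters the row above 37.5 and the axillary infant does not. That replaces one asymmetry with another, so the category should be assigned, not a temperature.

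**The case against.** The best defence is that grade 0 is not forced by the text. SAP 10.1.3.5 applies the rectal scale to temperatures measured rectally, and here nothing was measured. The 37.5°C only glosses the lowest intensity category, next to grade 1 for other symptoms. The rectal scoring exists to bring those results together with the other routes, and Template 19 reports a single axillary temperature block. A sensible programmer would assign grade 1 throughout. The documents also do not say how route is set when no temperature was recorded, so a rectal subgroup might not be identifiable.

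This is a fair reading and probably what was intended. It does not remove the problem. The text gives a number, the number is graded differently by route, and nothing in the SAP rules out the literal derivation. If grade 1 is meant, the rule should say so. Nor does this reading settle the conflict in step 4.

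A reader might go further and infer that a documented rectal fever is scored as no fever, and that the any-fever rate is therefore too low, by an amount that varies with the route each country uses. The documents do not support that. The numerator table counts the infant under 'Any' whatever the temperature or route, so the any-fever rate does not move if that table governs. The documents give no frequency of fevers without a temperature, no share of rectal readings and no route by country.

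**Conclusion.** The point holds in a limited form. The value 37.5°C is wrong as the lowest fever category for rectal readings. If graded on the rectal scale, it removes the infant from 'At least grade 1' and from any fever count built on the imputed temperature. Separately, the two parts of SAP 10.1.2.3.2 conflict on all routes about whether such infants enter the grade rows.

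The size cannot be computed from the documents. On the any-fever row the effect is zero provided the numerator table governs and, as I read it, Template 19's row for all fevers is that table's 'Any' category. The effect on 'At least grade 1' depends on three things the documents do not give: how many fevers are marked present without a value, how many of those are rectal, and whether route is known for them. The rule is the same in both groups and all analyses are descriptive, so no group difference is shown and no decision rests on this. It is a minor correction, worth making because it is cheap.

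**What to change.** In SAP 10.1.2.3.2:

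1. Replace the 37.5°C value with grade 1 for fever, whatever the route. Assign the category only, so that no imputed temperature feeds the 0.5°C increment rows. This also covers an unknown route.
2. State that the infant counts in the 'Any' fever row, as the numerator table already provides.
3. Reconcile the two parts of the section for infants with no daily value. Either they enter 'At least grade 1', and the sentence keeping missing recordings out of the grade rows gets an exception for them, or they count under 'Any' only, and the assignment to a lowest grade is dropped, which makes change 1 unnecessary. The first keeps the evident purpose of the closing list. The choice applies to every graded solicited symptom.

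The cost is a sentence or two in the SAP and about one line of derivation code. No new data are needed. The 37.5°C rule appears only in the SAP, so the protocol does not change.

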10.1.2.4. Unsolicited adverse events

Missing severity, relationship with study vaccine, and outcome of unsolicited adverse events will not be replaced and will appear as 'UNKNOWN' in all statistical output.

10.1.3. Data derivation**10.1.3.1. Age at vaccination in months**

When age at vaccination is to be displayed in months, it will be calculated as the number of complete calendar months between the date of birth (DOB) and the date of vaccination. For example:

DOB = 10JUN2017, Date of vaccination = 09JUL2018 -> Age = 12 months

DOB = 10JUN2017, Date of vaccination = 10JUL2018 -> Age = 13 months

10.1.3.2. Weight

Weight will be presented in kilograms. Weights reported in pounds will be converted as follows:

Weight in kilograms = Weight in pounds / 2.2. The result is rounded to 2 decimals.

10.1.3.3. Height

Height will be presented in centimeters. Heights reported in feet and inches will be converted as follows:

Height in centimeters = Height in inches x 2.54 The result is rounded to the unit (ie no decimal).

10.1.3.4. Body mass index (BMI)

BMI will be calculated as follows:

$$\text{BMI} = (\text{Weight in kilograms}) / (\text{Height in meters})^2$$

10.1.3.5. Temperature

- Temperatures will be presented in degrees Celsius (°C). Temperatures reported in degrees Fahrenheit (°F) will be converted as follows:

$$\text{Temperature (Celsius)} = ((\text{Temperature (Fahrenheit)} - 32) \times 5) / 9$$

The result is rounded to 1 decimal.

- The intensity of fever measured by oral, axillary or tympanic route will be scored as defined in the protocol. If in case, measured by rectal route, then the scoring will be performed as below to integrate the results with the other routes.

0	<38°C
1	≥38.0°C to ≤39.0°C
2	>39.0°C to ≤40.0°C
3	>40.0°C

